	
examination will be performed. Samples will be collected for FIX and human leukocyte antigen genotyping; HIV, HBV, and HCV status; FIX inhibitor determination; AAVrh10 binding antibody immunoglobulin G (IgG) assay; AAVrh10 neutralizing antibody testing; FIX activity; clinical laboratory assessments (hematology, coagulation, clinical chemistry, and urinalysis); and record spontaneous bleeding episodes and recombinant FIX use.
 
Day 0 – DTX101 Infusion
 
Subjects will be admitted for DTX101 administration and for continuous safety monitoring. Subjects will be discharged 24 hours after completion of the infusion.
 
Prior to dosing, blood samples will be collected for FIX inhibitor determination, AAVrh10 binding antibody IgG assay, AAVrh10 neutralizing antibody testing, FIX activity, cell-mediated immune response to AAVrh10 and FIX, and clinical laboratory assessments (hematology, coagulation, and clinical chemistry). Saliva, urine, and stool samples will be collected for assessment of viral shedding. An ECG (in triplicate) and a targeted physical examination will be performed. Vital sign measurements and weight will be recorded. The use of concomitant medications, spontaneous bleeding episodes and recombinant FIX use will be recorded.
 
Subjects will be provided a paper or electronic diary (eDiary). The subject will complete the EQ-5D-5L and the Haem-A-QoL questionnaires.
 
After dosing, a sample will be collected for clinical laboratory assessments (hematology and clinical chemistry) at 0.5, 4, and 8 hours after the start of infusion. Vital sign measurements will be recorded at 5 minutes after the start of infusion, and at 0.5, 1, 2, 4, 6, 8, and 22 hours after the start of infusion. A single 12-lead ECG will be performed at 1 hour after the start of infusion.
 
At All Visits (Day 1 Through Week 52)
 
Subjects will be asked to visit the study site approximately every 4 days through Week 12. Following the Week 12 visit, subjects will visit the study site once every 4 weeks through Week 52 or

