	
their early withdrawal from the study.
 
At each visit, samples will be collected for FIX activity and clinical laboratory assessments (hematology, coagulation, and clinical chemistry). Vital sign measurements will be recorded. Adverse events and SAEs will be monitored; concomitant medications, therapies, and procedures will be recorded; and the paper or eDiary will be reviewed with the subject.
 
Clinic or Home Visits
 
Subjects will be asked to provide clinical laboratory samples approximately every 4 days through Week 12 of the study. If subjects cannot visit the study site in person, subjects can be visited by clinically trained and qualified personnel approximately every 4 days at their home through Week 12, the exception being those weeks when a site visit is scheduled, to collect a clinical laboratory sample to monitor liver function tests (LFTs). Saliva, urine, and stool samples will also be collected for assessment of viral shedding on Days 8, 20, 36, 48, 64, and 76. These samples will continue to be collected until 3 consecutive negative results are obtained from each sample matrix.
 
Weeks 2, 4, 6, 8, 10, and 12
 
Saliva, urine, and stool samples will be collected for assessment of viral shedding. These will continue to be collected until 3 consecutive negative results are obtained from each sample matrix. Subjects will be asked to provide a sample for urinalysis (Weeks 2, 4, 6, 8, and 12).
 
In order to accurately assess vector-derived FIX activity as a result of DTX101 infusion, subjects will stop taking FIX prophylactically prior to the assessment of peak FIX activity at Week 6 and transition to an on-demand regimen for the remainder of the study. Subjects prophylactically using traditional recombinant FIX will be asked to begin the washout period starting at Week 5. Due to the longer half-life, subjects prophylactically taking long-acting recombinant FIX (eg, Alprolix) will be asked to begin the washout period starting at Week 3.

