3.2.2 Treatment Period

Subjects will be admitted for DTX101 administration and for continuous safety monitoring ([Section 8.2](#)). Subjects will be discharged 24 hours after completion of the infusion.

On Day 0, subjects will be provided a paper or an electronic diary (eDiary), depending on availability, to record bleeding episodes and use of recombinant FIX replacement therapy during the study. The diary will be reviewed with the subject at each visit.

Subjects will be asked to visit the clinic every 4 days through Week 12. Following the Week 12 visit, subjects will visit the study site once every 4 weeks through Week 52 or early withdrawal from the study.

Subjects will be asked to provide clinical laboratory samples approximately every 4 days through Week 12 of the study. If subjects cannot visit the study site in person, subjects can be seen by clinically trained and qualified personnel approximately every 4 days at their home through Week 12, the exception being those weeks when a site visit is scheduled, to collect a clinical laboratory sample to monitor LFTs. Saliva, urine, and stool samples will also be collected for assessment of viral shedding on Days 8, 20, 36, 48, 64, and 76. These samples will continue to be collected until 3 consecutive negative results are obtained from each sample matrix ([Table 15–2](#)).

[figure not shown]

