15.1 Appendix: Schedules of Events

Table 15–1 Schedule of Events – Scheduled Clinic Visits

Procedure	Period	Screening	Dosing	Treatment Period: Week 2 through Week 52 (includes clinic or home visits [see Table 15–2])							Unscheduled	End of Study/Early Withdrawal
	Week	Days –30 to –1	Day 0	2	4	6	8	10	12	16–48 ^a		
	Visit Window (Days)	-	-	±2	±2	±2	±2	±2	±2	±4	-	±7
Informed consent		X										
Demographics		X										
Medical history		X										
Hemophilia history		X										
Prior medication / therapies / procedures		X										
Review of eligibility criteria		X										
FIX genotyping		X										
HLA genotyping		X										
HBV, HCV, and HIV status		X										
FIX inhibitor (Bethesda assay)		X	X ^b			X	X			X ^c	X ^d	X

Procedure	Period	Screening	Dosing	Treatment Period: Week 2 through Week 52 (includes clinic or home visits [see Table 15-2])							Unscheduled	End of Study/Early Withdrawal
	Week	Days -30 to -1	Day 0	2	4	6	8	10	12	16-48 ^a		
	Visit Window (Days)	-	-	±2	±2	±2	±2	±2	±2	±4	-	±7
Coagulation panel (PT/INR, D-dimer assay, aPTT)	X	X ^b	X	X	X	X	X	X	X	X ^d	X	
AAVrh10 neutralizing antibody test (ELISA)	X	X ^b			X	X				X ^c	X ^d	X
Cell-mediated immune response to AAVrh10 and FIX (ELISPOT assay)		X ^b			X	X				X ^c	X ^d	X
AAVrh10 binding antibody IgG assay (ELISA)	X	X ^b			X	X				X ^c	X ^d	X
Saliva, urine, and stool for viral shedding (qPCR) ^f		X ^e	X	X	X	X	X	X	X	X ^d		X
FIX activity (aPTT clot-based assay)	X	X ^b	X	X	X	X	X	X	X	X ^d		X
Hematology / clinical chemistry ^g	X	X ^h	X	X	X	X	X	X	X	X ^d		X
Urinalysis	X		X	X	X	X		X		X ^d		X

Procedure	Period	Screening	Dosing	Treatment Period: Week 2 through Week 52 (includes clinic or home visits [see Table 15-2])							Unscheduled	End of Study/Early Withdrawal
	Week	Days -30 to -1	Day 0	2	4	6	8	10	12	16-48 ^a		
	Visit Window (Days)	-	-	±2	±2	±2	±2	±2	±2	±4	-	±7
12-lead ECG		X	X ⁱ									X
Vital sign measurements (heart rate, blood pressure, respiratory rate)		X	X ^j	X	X	X	X	X	X	X	X	X
Height and weight ^k		X	X ^{b,1}									X ^l
Complete physical examination		X										X
Targeted physical examination ^m			X ^b			X			X	X ⁿ		
AE/SAE monitoring	X	X	X	X	X	X	X	X	X	X	X	X
Concomitant medications / therapies / procedures		X ^b	X	X	X	X	X	X	X	X	X	X
Diary distributed			X									
Diary reviewed				X	X	X	X	X	X	X	X	X
Diary returned												X

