Procedure	Period	Screening	Dosing	Treatment Period: Week 2 through Week 52 (includes clinic or home visits [see Table 15-2])							Unscheduled	End of Study/Early Withdrawal
	Week	Days -30 to -1	Day 0	2	4	6	8	10	12	16-48 ^a		
	Visit Window (Days)	-	-	±2	±2	±2	±2	±2	±2	±4	-	±7
Record of spontaneous bleeding episodes		X	X ^b	X	X	X	X	X	X	X	X	X
Record recombinant FIX use		X	X ^b	X	X	X	X	X	X	X	X	X
Prophylactic recombinant FIX washout		X ^o				X ^{p, q}				X ^{r, s}		X ^{r, s}
EQ-5D-5L QoL questionnaire			X ^b							X ⁿ		X
Haem-A-QoL questionnaire			X ^b							X ⁿ		X
DTX101 infusion			X									

Abbreviations: AAVrh10, adeno-associated virus serotype rh10; AE, adverse event; aPPT, activated partial thromboplastin time; ECG, electrocardiogram; ELISA, enzyme-linked immunosorbent assay; ELISPOT, enzyme-linked immunospot; EQ-5D-5L, EuroQoL 5D 5 level; FIX, factor IX; Haem-A-QoL, Haemophilia-Specific Quality of Life; HBV, hepatitis B virus; HCV, hepatitis C virus; HIV, human immunodeficiency virus; HLA, human leukocyte antigen; IgG, immunoglobulin G; INR, international normalized ratio; PT, prothrombin time; QoL, quality of life; qPCR, quantitative polymerase chain reaction; SAE, serious adverse event.

- Following the Week 12 visit, subjects will return to the study site once every 4 weeks starting at Week 16.
- To be collected before DTX101 administration.
- Samples to be obtained at Weeks 16, 32, 40, and 48.

- d. A laboratory parameter may be repeated if there is any concern about the values obtained. Laboratory values must be repeated if ≥ 2 -fold the upper limit of normal or ≤ 0.5 -fold the lower limit of normal.
- e. Saliva and urine samples for viral shedding to be collected before DTX101 administration. Subjects will be provided with an appropriate container to collect a stool sample at home prior to the visit.
- f. Samples for viral shedding to be collected at Weeks 2, 4, 6, 8, 10, and 12 and on Days 8, 20, 36, 48, 64, and 76 (see Table 15-2) until negative on 3 consecutive occasions for each sample matrix.
- g. Hematology to include: complete blood count and differential. Clinical chemistry to include: sodium, potassium, chloride, carbon dioxide, blood urea nitrogen, creatinine, glucose, calcium, phosphate, magnesium, albumin, total protein, creatine kinase, bilirubin (total and indirect), alanine aminotransferase, aspartate aminotransferase, alkaline phosphatase, gamma-glutamyl transferase, and lactate dehydrogenase.

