Table 15–2 Schedule of Events – Clinic or Home Visits During the Treatment Period

Procedure	Visit Window (Days)	Treatment Period										
		4	8	20	24	32	36	48	52	60	64	76
		± 1	± 1	± 1	± 1	± 1	± 1	± 1	± 1	± 1	± 1	± 1
Clinical chemistry ^{a, b}		X	X	X	X	X	X	X	X	X	X	X
Saliva, urine, and stool for viral shedding (qPCR) ^{c, d}			X	X			X	X			X	X

Abbreviations: qPCR, quantitative polymerase chain reaction.

- Clinical chemistry to include: sodium, potassium, chloride, carbon dioxide, blood urea nitrogen, creatinine, glucose, calcium, phosphate, magnesium, albumin, total protein, creatine kinase, bilirubin (total and indirect), alanine aminotransferase, aspartate aminotransferase, alkaline phosphatase, gamma-glutamyl transferase, and lactate dehydrogenase.
- A laboratory parameter may be repeated if there is any concern about the values obtained. Laboratory values must be repeated if ≥ 2 -fold the upper limit of normal or ≤ 0.5 -fold the lower limit of normal.
- Subjects will be provided with an appropriate container to collect a stool sample at home prior to the visit.
- Samples for viral shedding to be collected at Weeks 2, 4, 6, 8, 10, and 12 (see Table Table 15–1) and on Days 8, 20, 36, 48, 64, and 76 until negative on 3 consecutive occasions for each sample matrix.

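### Clinical chemistry is stated as about every 4 days through Week 12, but the schedule tables as read have no draw between Day 76 and Day 84 (minor)

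*Protocol*

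**What the plan says.** Protocol 3.2.2 sets the sampling frequency: "Subjects will be asked to provide clinical laboratory samples approximately every 4 days through Week 12 of the study". The same section also says, without any hedge, "Subjects will be asked to visit the clinic every 4 days through Week 12". Where a subject cannot attend, staff may draw the liver function sample at home at about the same frequency, "the exception being those weeks when a site visit is scheduled". The Synopsis carries the same message: "Subjects will be asked to visit the study site approximately every 4 days through Week 12", or, failing that, subjects can be "visited by clinically trained and qualified personnel approximately every 4 days at their home through Week 12".

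The days themselves are fixed elsewhere. Section 3.2 refers to Tables 15-1 and 15-2 for timing, Section 8.2.6 has samples taken at the time points in those tables, and Section 13.2.2 calls adherence to them essential. Table 15-1 covers the scheduled clinic visits. Table 15-2 covers the visits in between and, for blood, lists clinical chemistry only. After that, "Following the Week 12 visit, subjects will return to the study site once every 4 weeks starting at Week 16".

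**The concern.** Sites will work from the tables, so what matters is whether the tables deliver the stated frequency. As read, they do so until Day 76 and then schedule no chemistry until the Week 12 visit on Day 84.

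The draws exist to monitor liver function. Under Section 8.2.6.2 steroid treatment depends on a measured ALT more than 1.5-fold above baseline, with a repeat within 24 hours of learning of it. A rise that nobody measures cannot start that process. The stopping rule in Section 3.2.4 for related Grade 2 toxicity lasting more than 7 days also relies on timely chemistry when the toxicity is a chemistry value. At nominal days, Day 76 to Day 84 is the only chemistry interval through Week 12 that exceeds those 7 days.

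**Working it through.** **Inputs**
- Table 15-1, row "Hematology / clinical chemistry": Day 0 and Weeks 2, 4, 6, 8, 10 and 12. At 7 days per week these are Days 0, 14, 28, 42, 56, 70 and 84, with a window of ±2 days after Day 0.
- Table 15-2, chemistry row: Days 4, 8, 20, 24, 32, 36, 48, 52, 60, 64 and 76, with a window of ±1 day.
- Stated interval: approximately 4 days.

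**1. Merge and difference**

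| Block | Chemistry days | Gaps (days) |
|---|---|---|
| Days 0 to 28 | 0, 4, 8, 14, 20, 24, 28 | 4, 4, 6, 6, 4, 4 |
| Days 28 to 56 | 28, 32, 36, 42, 48, 52, 56 | 4, 4, 6, 6, 4, 4 |
| Days 56 to 84 | 56, 60, 64, 70, 76, 84 | 4, 4, 6, 6, 8 |

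There are ten gaps of 4 days, six of 6 and one of 8. The mean is 84/17 = 4.94 days. The first two blocks repeat exactly (+4, +8, +14, +20, +24, +28). The third lacks only the +24 draw, which is 56 + 24 = Day 80. Adding it makes the third block 4, 4, 6, 6, 4, 4, with a mean of 84/18 = 4.67 days and a maximum of 6.

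**2. Windows.** Day 76 (±1) to Day 84 (±2) spans 8 − 3 = 5 to 8 + 3 = 11 days. With Day 80 added, the longest permitted interval is a 6-day gap at 6 + 1 + 2 = 9 days.

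**3. Does the exception for site-visit weeks explain it?** The protocol does not say how a visit week is counted, so take three readings.
- Seven days ending on the visit: Weeks 2, 4, 6, 8 and 10 each hold a Table 15-2 draw (Days 8, 24, 36, 52, 64). Only Week 12 (Days 78 to 84) holds none, so the exception was not applied in this way.
- Seven days starting on the visit: Days 20, 32, 48, 60 and 76 fall in visit weeks and are drawn, while Day 80 falls outside one.
- Visit day ±3: all 11 Table 15-2 draws fall outside visit weeks, in pairs (4/8, 20/24, 32/36, 48/52, 60/64). Only Days 74 to 80 hold a single draw, Day 76. This reading accounts for the 6-day gaps and still calls for Day 80.

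None of the three explains the missing draw.

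**4. Size.** Assume that a rise starts at a uniformly random time and shows at the next scheduled draw. With gaps g, the mean wait is Σg² / (2Σg).

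| Onset within | As read | With Day 80 |
|---|---|---|
| Days 0 to 84 | 440/168 = 2.62 days | 408/168 = 2.43 days |
| Days 56 to 84 | 168/56 = 3.00 days | 136/56 = 2.43 days |
| Days 76 to 84 | 64/16 = 4.0 days | 32/16 = 2.0 days |

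The share of onset times that wait more than 6 days falls from (8 − 6)/84 = 2.4% to 0.

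**5. Visit count.** Section 3.2 expects about 30 site visits. The tables give 1 screening + 1 dosing + 6 (Weeks 2 to 12) + 9 (Weeks 16 to 48) + 1 (Week 52) = 18, plus 11 from Table 15-2 = 29, or 30 with Day 80. Both fit, so the count does not settle whether a Day 80 visit was intended.

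**The case against.** **The table may have been damaged in reading.** The day, window and chemistry rows of Table 15-2 each have 11 entries, so scattered cell loss is unlikely. A whole last column could still have dropped out and left the rows in agreement. By the pattern, Day 80 would be a chemistry-only day, so the viral-shedding days listed elsewhere cannot confirm or exclude it. The SAP reproduces only Table 15-1. This objection stands, and it is why the source table must be checked first.

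**Existing safeguards shorten the delay.** Section 8.2.5 has significantly abnormal results repeated until they return to normal or baseline. Section 8.2.6 requires a repeat at 2-fold the upper limit of normal or above, and Table 15-1 has an unscheduled column that covers chemistry. This also stands. What remains exposed is a new rise after Day 76, or one too small at Day 76 to prompt a repeat.

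**Stronger readings that the documents do not support**
- A reader might infer that every laboratory-based stopping rule is delayed. Hematology and the coagulation panel do not appear in Table 15-2. In the tables they follow the clinic visits, already 14 days apart through Week 12, and a Day 80 chemistry draw would not change that.
- A reader might infer that the 6-day gaps are errors too, and that every sentence giving the frequency must be rewritten. The word approximately reasonably covers 6 days. It does not reasonably cover a single interval of twice the stated length in an otherwise regular pattern.
- A reader might infer a major safety gap. The fivefold-ALT stopping rule covers only the first 8 weeks and is unaffected. The interval also falls after the Week 6 primary assessment and the committee review. From Week 12 the plan itself moves to 28-day intervals under the same steroid trigger.

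**Conclusion.** Wrong as written, and minor, subject to the source-table check. The text states a chemistry frequency that the tables as read miss once, in an 8-day interval from Day 76 to Day 84. This is the only chemistry interval through Week 12 longer than 6 days, and it looks like an omitted Day 80 draw: the pattern breaks only there and the protocol gives no reason for it.

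The consequence is later detection of a new or small ALT rise, or another chemistry abnormality, in that one interval. A Day 80 draw would shorten the mean wait by 2 days for onset inside it and by 2.62 − 2.43 = 0.19 days over Days 0 to 84. These waits assume uniform onset, nominal visit days and no unscheduled testing. No endpoint, dose decision or analysis is shown to change.

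**What to change.** 1. Check the source Table 15-2 for a Day 80 column.
2. If there is none, add a Day 80 (±1) clinical chemistry draw to Table 15-2. This costs one column and one clinic or home draw per subject, 12 to 18 draws in total for the planned 12 to 18 subjects, under the arrangement already in place.
3. In either case, change the unhedged clinic-visit sentence in Section 3.2.2 to say approximately every 4 days, in the clinic or at home. The other sentences that give the frequency are already hedged and can stand.

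If the source table already shows Day 80, only the third step remains.

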3.2.3 Prophylactic Factor IX Washout Periods

3.2.3.1 Screening Period

If the subject does not have a documented history of FIX activity, a blood sample will be needed to confirm the severity of hemophilia B for inclusion ([Section 4.1](#)) after washout of recombinant FIX ([Figure 3–2](#)). For subjects taking long-acting recombinant FIX prophylactically to prevent bleeding episodes, the washout period is to start at approximately Day –29 and last for 21 days (approximately Day –8). For subjects taking traditional recombinant FIX prophylactically to prevent bleeding episodes, the washout period is to start at approximately Day –29 and last for 7 days (approximately Day –22). The blood sample must be obtained and results available prior to dosing on Day 0. Subjects can then transition

back onto their prophylactic regimen until the washout period during the treatment period (prior to Week 6) is to begin ([Section 3.2.3.2](#)).

NOTE: This washout period is not needed for subjects with a documented history of FIX activity.

Figure 3–2**Recombinant FIX Washout During the Screening Period**

Abbreviations: FIX, factor IX.

[figure not shown]
- a. Washout required for subjects that do not have a documented history of FIX activity to meet eligibility criterion (ie, $\leq 2\%$ of normal).
- b. Following assessment of FIX activity, subjects can transition back on to their prophylactic regimen until the protocol mandated washout period prior to the Week 6 assessment of FIX activity.

3.2.3.2 Treatment Period

In order to accurately assess vector-derived FIX activity as a result of DTX101 infusion, subjects will stop taking FIX prophylactically prior to the assessment of peak FIX activity at Week 6 and transition to an on-demand regimen for the remainder of the study. Subjects prophylactically using traditional recombinant FIX will be asked to begin the washout period starting at Week 5. Due to the longer half-life, subjects prophylactically taking long-acting recombinant FIX (eg, Alprolix) will be asked to begin the washout period starting at Week 3 ([Figure 3–3](#)).

If, at any time during the study, a subject experiences bleeding episodes frequent enough to consider prophylactic treatment, the investigator will discuss treatment options with the medical monitor. If a subject resumes prophylactic FIX replacement therapy, as rescue treatment after Week 6, additional washout periods prior to Week 24 and Week 52 will also be performed. Subjects prophylactically using traditional recombinant FIX will be asked to begin the washout period starting at Week 23 and Week 51. Due to the longer half-life, subjects taking long-acting recombinant FIX (eg, Alprolix) will be asked to begin the washout period starting at Week 21 and Week 49 (Figure 3–3).

Figure 3–3 Recombinant FIX Washout During the Treatment Period

Abbreviations: FIX, factor IX.

- a. Following washout, subjects will be transitioned to an on-demand regimen for the remainder of the study.
- b. Washout needed if, at any time during the study after Week 6, a subject experiences bleeding episodes frequent enough to consider re-initiating prophylactic treatment.

The on-demand use of recombinant FIX is not prohibited and may be used at any time during the study. Subjects will be asked to record this use as outlined in [Section 8.1.3](#).

3.2.4 Safety Stopping Criteria

Enrollment will be suspended and the study will be discussed with regulators if, at any time during the study, any of the following occur:

- Death of a subject, at any time, that is considered related to DTX101 by the investigator,
- Fivefold increase in baseline (predose, Day 0) ALT within 8 weeks after vector infusion that is considered related to DTX101 by the investigator,
- Grade 2 toxicity develops that persists for more than 7 days and is considered related to DTX101 by the investigator,
- At least Grade 3 toxicity develops, including an infusion-related reaction \geq Grade 3, that is considered related to DTX101 by the investigator, or
- Occurrence of a malignancy, at any point after administration of vector, that is considered related to DTX101 by the investigator.

Abnormal clinically significant laboratory values (hematology, coagulation panel, and clinical chemistry) as assessed by the investigator will be considered AEs. Laboratory values that meet any of the above criteria will result in the suspension of the study.

Any event that meets the above criteria will be reported immediately as outlined in [Section 9.1.2.2](#), and the appropriate pages of the electronic case report form (eCRF) must be completed. Enrollment and dosing will be temporarily suspended until the situation can be assessed and risks to subjects mitigated. If study enrollment is suspended, all subjects who have been enrolled will remain in the study and will continue to be monitored through their completion or withdrawal from the study.

